TITLE: Strength Training and Endurance Exercise for LIFE

Trial # NCT02102060
Registered 3/27/2014

Principal Investigators

[name], ScM,^{1,2}
[name]^{3,4}

1 Salem Veterans Affairs Medical Center, Salem, Virginia

2 Virginia Tech Carilion School of Medicine, Roanoke, Virginia

3 Baltimore Veterans Affairs Medical Center Geriatric Research, Education, and Clinical Center at the Veterans Affairs Maryland Health Care System

4 University of Maryland School of Medicine, Baltimore, Maryland

Funding

The research described here was supported by the Department of Veterans Affairs Veterans Health Administration, Rehabilitation Research and Development Service, I01 RX000667

Ethics approval and consent to participate

The study was approved by the Institutional Review Boards at the Salem VAMC, Salem, VA and the University of Maryland IRB, Baltimore, MD.

Written informed consent was obtained from each patient prior to participation.

Protocol Overview

Hypothesis: We hypothesize that high-intensity exercise training will increase cardiorespiratory fitness, which will be mediated by improved diastolic function and will correlate with decreased biomarkers of inflammation.

Background: Adults with HIV on antiretroviral therapy have a life expectancy approaching that of the general population yet have impaired cardiorespiratory fitness and diastolic function that increase their risk for age-related disability. Chronic inflammation is a well-studied mediator of advanced aging with HIV, including cardiac dysfunction, yet the impact of exercise training is unclear. The study objective is to develop an exercise program for older adults with HIV that targets pathophysiological processes of advanced aging and will prevent and improve disability.

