Design: The study is a randomized trial comparing 16-weeks of progressive aerobic and resistance training to usual care in sedentary older (50+ years) adults with HIV. The center-based exercise training is performed three times weekly under supervision. The end-target duration and intensity of aerobic exercise is 45 minutes at 70-80% of baseline heart rate reserve. Resistance training progresses from low-intensity to high-intensity based on initial one repetition maximum (1-RM) in the three upper body (chest press, seated row, pull-down) and three lower body exercises (leg press, knee extension, knee flexion). Primary outcomes are cardiorespiratory fitness, cardiac function, and biomarkers of myocardial fibrosis and cardiac stress. Secondary outcomes include muscle strength, body composition measured by Dual-energy X-ray absorptiometry (DXA), and biomarkers of systemic Inflammation.

Statistical Analysis Plan (SAP)

Power Analyses

Power calculations were based on results from randomized exercise trials that included a sedentary control group. For outcomes of diastolic function¹, cytokines², and biomarkers of myocardial fibrosis³ we used mean (SD) from exercise trials in older adults without HIV since results were not available for adults with HIV. Referenced values for VO₂peak⁴ and strength⁵ were obtained from trials in adults with HIV, but a younger population (mean age 30-45 years old). For these outcomes, a sample size of 22 participants per group provides at least 80% power to detect a between group difference with a two-sided alpha of 0.05. We acknowledge that older participants may have greater muscle soreness or fatigue as well as more medical problems. Therefore, our target enrollment number assumes a conservative attrition rate of 30% based on prior exercise interventions in adults with HIV.^{6,7}

Statistical Analyses

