ANOVA will be used to compare the change in the intervention group to the change in the control group for the following primary outcomes, AIM 1: (1) functional performance, (2) aerobic capacity, (3) diastolic function; AIM 2: (1) strength, (2) muscle mass. In the ANOVA models, the change from baseline to 16-weeks will be the dependent variable in models adjusted for the baseline value of the outcome measure and treatment group. Groups will be compared at baseline for differences in potential confounders such as age and comorbidity. Additional adjustment will be made if the randomization produces groups that are not balanced on factors which are also associated with outcomes. We do not anticipate needing to adjust for sex, history of AIDS, or length of HIV infection (CD4 cell count) as our group assignment will be blocked on these factors. Similar analyses will be performed for secondary outcomes, intramuscular fat,

percent body fat, plasma glucose, insulin, and lipids, blood pressure. All analyses will be two-tailed.

We will use regression analyses to test the following associations, Specific aim 1: change (16-week value minus baseline value) in VO₂peak with change in (1) diastolic function and (2) markers of systemic chronic inflammation, (3) change in diastolic function with change in myocardial fibrosis; Specific Aim 2 (1) change in strength with change in muscle mass, (2) change in muscle mass with change in markers of inflammation, change in intramuscular fat with change in (3) plasma lipid and (4) fasting glucose concentrations. These analyses will be adjusted as noted above, except they will not be adjusted for group as the analytic interest lies in the relation of change to change, not change to group.

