Analyses will include subjects who drop out before completion of the 16-week study period by way of multiple imputation. This intention to treat approach will investigate factors that may affect compliance and difficulty with exercise training, including pain/soreness and medical comorbidity. If the pattern of missing data is missing completely at random, or simply at random, our multiple imputation should eliminate bias due to loss to follow-up. Because the majority of the subjects will be recruited from the Salem VA HIV clinic, we will be able to obtain clinical data from subjects who drop out of the study, but remain in clinical care, to determine if drop-out was related to medical conditions that may influence outcomes. Thus, we will be able to estimate bias introduced by loss to follow-up. If there is sufficient information, we may be able to model the drop-out process and adjust our analyses for loss to follow-up even if the missing data pattern is non-ignorable. If 48 training sessions cannot be completed in 16 weeks, then total training time will be tracked, and incorporated into the data analysis.

Data management

A robust data management plan is in place to ensure the accuracy, completeness, legibility, and timeliness of the data collected across the two sites. The study data is managed carefully to ensure its integrity. Ongoing quality assurance activities include summary statistics to identify outliers that are then confirmed with source documents. To maintain participant confidentiality, each participant is assigned a numerical ID which is used on all case report forms, data sheets and surveys. The keycode to link individuals with their assigned IDs are stored in locked cabinets and computer folders separate from study data. Data is entered directly from the source documents into data spreadsheets that are stored in limited access study folders on the VA server that can be accessed only through a password protected VA computer from either site.

REFERENCES

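### Site is in none of the stated models of this two-site trial; a prespecified site term costs almost nothing and matters most for the change-to-change regressions

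*Combined protocol and SAP*

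**What the plan says.** The document describes a two-site trial. Data management speaks of the "timeliness of the data collected across the two sites", and ethics approval came from the "Institutional Review Boards at the Salem VAMC, Salem, VA and the University of Maryland IRB, Baltimore, MD". The Design paragraph adds: "The center-based exercise training is performed three times weekly under supervision". The missing-data text under Statistical Analyses expects that "the majority of the subjects will be recruited from the Salem VA HIV clinic", and gives no numerical share.

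On allocation, Statistical Analyses states: "We do not anticipate needing to adjust for sex, history of AIDS, or length of HIV infection (CD4 cell count)", the reason being "as our group assignment will be blocked on these factors". Site is not in that list, and there is no separate randomisation section.

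On the models, the change to 16 weeks is analysed "in models adjusted for the baseline value of the outcome measure and treatment group". The change-to-change regressions take the same adjustment without group. Any further covariate depends on this rule: "Additional adjustment will be made if the randomization produces groups that are not balanced on factors which are also associated with outcomes". Age and comorbidity are given as examples. The rule sets no threshold for imbalance or for association.

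**The concern.** Site is known for every participant before any outcome is seen, and it can plausibly affect how training is supervised and how outcomes are measured. Leaving it out has three possible consequences.

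- Any difference between sites in mean change that baseline does not explain stays in the residual variance and lowers power.
- Whether site is adjusted for is decided after looking at the data, by a rule without thresholds.
- The regressions of one change on another, which carry the hypotheses on diastolic function and inflammation, are observational within the trial. If both changes differ by site, site alone can produce an association. The imbalance rule looks at treatment groups, so it does not address this.

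**Working it through.** **Inputs from the documents (Power Analyses).** 22 per group, at least 80% power, two-sided alpha 0.05. No difference or SD is given, so the stated power cannot be reproduced forward. Solving backwards with the noncentral t on 42 degrees of freedom, 22 per group has 80% power for a standardised difference of 0.865.

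**Assumptions.** The documents give neither a site split nor a site effect. I take a 70:30 split and let s be the site difference in mean change, given baseline, in units of the within-site SD. The power calculation is a two-group t-test, with one further degree of freedom removed when site is added. It stands in for the planned baseline-adjusted model.

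**1. Power for the treatment comparison.** Between-site variance is 0.7 × 0.3 × s² = 0.21s², so total variance is 1 + 0.21s². If the planning SD is the total SD, removing the site variance raises the standardised difference from 0.865 to 0.865 × √(1 + 0.21s²), on 41 degrees of freedom.

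| s | Share of variance, 0.21s²/(1 + 0.21s²) | Power without site | Power with site |
|---|---|---|---|
| 0 | 0% | 80.0% | just under 80.0% |
| 0.25 | 0.0131/1.0131 = 1.3% | 80.0% | 80.5% |
| 0.5 | 0.0525/1.0525 = 5.0% | 80.0% | 81.9% |
| 1.0 | 0.21/1.21 = 17.4% | 80.0% | 86.9% |

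When site has no effect, the lost degree of freedom costs less than 0.1 point. If the planning SD is instead the within-site SD, power with a site term is about 80%. Leaving site out then lowers it to 79.5%, 78.0% and 72.1% for s = 0.25, 0.5 and 1.0.

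**2. Validity of the treatment comparison.** Simulation with 44 participants and about 32% at the smaller site:

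| Allocation and model | Type I error, s = 0.5 | Type I error, s = 1.0 |
|---|---|---|
| Not blocked by site, site not modelled | 5.2% | 4.9% |
| Not blocked by site, site modelled | 5.1% | 4.7% |
| Blocked by site, site not modelled | 4.5% | 3.0% |
| Blocked by site, site modelled | 4.9% | 5.0% |

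The planned test does not exceed its level. If allocation was in fact blocked by site, omitting site from the model makes the test conservative, so a site term is appropriate either way.

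**3. Change-to-change regressions.** Suppose two changes are unrelated within site but both are shifted by s at one site. The correlation induced by site is 0.21s²/(1 + 0.21s²), which is 0.05 at s = 0.5 and 0.17 at s = 1.0. Simulated false-positive rates with 44 participants and a 70:30 split, without baseline covariates, were:

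- s = 0.5: about 6.5% (runs between 6.2% and 6.5%) without site;
- s = 1.0: about 21% (runs between 20% and 21%) without site;
- either value of s: about 5% with a site term.

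**The case against.** The best reply is that the gain may be very small. Every figure rests on an assumed split and an assumed site effect. The planned models already adjust for the baseline outcome, which absorbs site differences in level due to equipment or case mix; only a difference in change given baseline remains. A 1.0 SD difference of that kind would exceed the 0.865 SD treatment difference that 22 per group can detect, and nothing in the documents suggests one. At 0.25 to 0.5 SD the gain is about 0.5 to 2 power points. All of this stands, and it is why the point is minor.

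It can also be said that the imbalance rule would bring site in when it matters, since its examples are not exhaustive. That is partly true for the treatment comparison, although only after an unspecified judgement on observed data. It does not hold for the regressions, because balance between treatment groups says nothing about site confounding of one change with another.

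A reader might infer three stronger things that the documents do not support.

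- That allocation was blocked on the named factors only. The text lists them to explain why adjustment is not expected. Blocking by site is unstated, not excluded.
- That the treatment estimate is biased. Chance imbalance in site is part of the random variation that the confidence interval covers, and type I error stays near 5%. A 15-point imbalance with a 1.0 SD site difference would shift that one estimate by 0.15 × 1.0 = 0.15 SD, but both conditions are needed.
- That omitting site necessarily widens the interval. It does so only if the sites differ in change given baseline.

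**Conclusion.** The point holds as a cheap improvement of minor severity. The plan names two sites and puts site in none of its stated models. The randomised comparison is valid as planned. The likely loss there is 0.5 to 2 power points for site differences of 0.25 to 0.5 SD, and about 7 points at 1.0 SD, under a 70:30 split and a planning SD that includes site variation.

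The stronger argument concerns the change-to-change regressions. Neither randomisation nor the imbalance rule protects them, and their false-positive rate could rise from about 5% to 6.5% or 21%. Those figures need a site shift of 0.5 or 1.0 SD in both changes, for which the documents offer no evidence either way.

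**What to change.** Add one sentence to Statistical Analyses: site (Salem or Baltimore) is a fixed covariate in every baseline-adjusted outcome model and every change-to-change regression, regardless of observed balance. Put site in the multiple imputation model too, so that the imputations respect the models they feed. Leave the randomisation scheme unchanged, and state whether it was blocked by site.

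The cost is one degree of freedom per model, worth under 0.1 power point if site has no effect. No new data are needed.
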